### **10.2 Informed consent procedures**

Eligible patients may only be included in the study after providing written (witnessed, where required by law or regulation), IRB/IEC-approved informed consent, or, if applicable after such consent has been provided by a legally acceptable representative(s) of the patient. In cases where the patient's representative gives consent, the patient must be informed about the study to the extent possible given his/her understanding. If the patient is capable of doing so, he/she must indicate assent by personally signing and dating the written informed consent document or a separate assent form. Informed consent must be obtained before conducting any study-specific procedures (e.g., all of the procedures described in the protocol). The process of obtaining informed consent must be documented in the patient source documents.

Novartis will provide to investigators in a separate document a proposed informed consent form that complies with the ICH GCP guideline and regulatory requirements and is considered appropriate for this study. Any changes to the proposed consent form suggested by the investigator must be agreed to by Novartis before submission to the IRB/IEC, and a copy of the approved version must be provided to the Novartis monitor after IRB/IEC approval.

Women of child bearing potential must be informed that taking the study treatment may involve unknown risks to the fetus if pregnancy were to occur during the study and agree that in order to participate in the study they must adhere to the contraception requirement for the duration of the study. If there is any question that the patient will not reliably comply, they must not be entered in the study.

### **10.3 Responsibilities of the investigator and IRB/IEC**

Before initiating a trial, the investigator/institution must obtain approval/favorable opinion from the Institutional Review Board/Independent Ethics Committee (IRB/IEC) for the trial protocol,

written informed consent form, consent form updates, subject recruitment procedures (e.g., advertisements) and any other written information to be provided to patients. Prior to study start, the investigator is required to sign a protocol signature page confirming his/her agreement to conduct the study in accordance with these documents and all of the instructions and procedures found in this protocol and to give access to all relevant data and records to Novartis monitors, auditors, Novartis Quality Assurance representatives, designated agents of Novartis, IRBs/IECs, and regulatory authorities as required. If an inspection of the clinical site is requested by a regulatory authority, the investigator must inform Novartis immediately that this request has been made.

#### **10.4 Publication of study protocol and results**

The key design elements of this protocol will be posted in a publicly accessible database such as [clinicaltrials.gov](http://clinicaltrials.gov). In addition, upon study completion and finalization of the study report the results of this trial will be either submitted for publication and/or posted in a publicly accessible database of clinical trial results.

#### **10.5 Quality Control and Quality Assurance**

Novartis maintains a robust Quality Management (QM) system that includes all activities involved in quality assurance and quality control, including the assignment of roles and responsibilities, the reporting of results, and the documentation of actions and escalation of issues identified during the review of quality metrics, incidents, audits and inspections.

Audits of investigator sites, vendors, and Novartis systems are performed by Novartis Pharma Auditing and Compliance Quality Assurance, a group independent from those involved in conducting, monitoring or performing quality control of the clinical trial. The clinical audit process uses a knowledge/risk based approach.

Audits are conducted to assess GCP compliance with global and local regulatory requirements, protocols and internal standard operating procedures (SOPs), and are performed according to written Novartis processes.

### **11 Protocol adherence**

This protocol defines the study objectives, the study procedures and the data to be collected on study participants. Additional assessments required to ensure safety of patients should be administered as deemed necessary on a case by case basis. Under no circumstances is an investigator allowed to collect additional data or conduct any additional procedures for any research related purpose involving any investigational drugs under the protocol.

Investigators ascertain they will apply due diligence to avoid protocol deviations. If an investigator feels a protocol deviation would improve the conduct of the study this must be considered a protocol amendment, and unless such an amendment is agreed upon by Novartis and approved by the IRB/IEC and health authorities, where required, it cannot be implemented.

## 11.1 Protocol amendments

Any change or addition to the protocol can only be made in a written protocol amendment that must be approved by Novartis, health authorities where required, and the IRB/IEC prior to implementation. Only amendments that are intended to eliminate an apparent immediate hazard to patients may be implemented immediately provided the health authorities are subsequently notified by protocol amendment and the reviewing IRB/IEC is notified. Notwithstanding the need for approval of formal protocol amendments, the investigator is expected to take any immediate action required for the safety of any patient included in this study, even if this action represents a deviation from the protocol. In such cases, the reporting requirements identified in [Section 7](#) Safety Monitoring must be followed.

## 13 Appendix 1: Clinically notable laboratory and ECG values

Certain adverse events should be considered medically significant and should be submitted to Novartis as SAEs within 24 hours.

### 1. Hepatic

- ALT or AST  $> 5 \times$  ULN  
ALP  $> 2 \times$  ULN (in the absence of known bone pathology)  
TBL  $> 2 \times$  baseline value
- ALT or AST  $> 3 \times$  ULN and INR  $> 1.5$
- Potential Hy's Law cases (defined as ALT or AST  $> 3 \times$  ULN and TBL  $> 2 \times$  ULN [mainly conjugated fraction] without notable increase in ALP to  $> 2 \times$  ULN)
- Any clinical event of jaundice (or equivalent term)
- ALT or AST  $> 3 \times$  ULN accompanied by (general) malaise, fatigue, abdominal pain, nausea, or vomiting, or rash with eosinophilia
- Any adverse event potentially indicative of a liver toxicity, like hepatic failure, fibrosis and cirrhosis and other liver damage-related conditions; non-infectious hepatitis, liver neoplasms

### 2. Cardiac

- Absolute QTcF  $> 500$  ms (confirmed by repeat ECGs)

## 14 Appendix 2: Liver event and Laboratory trigger Definitions and Follow-up Requirements

**Table 14-1 Liver event and laboratory trigger definitions**

	Definition/ threshold
LIVER LABORATORY TRIGGERS	
 
• <math>3 \times \text{ULN} < \text{ALT} / \text{AST} \leq 5 \times \text{ULN}</math>
 
• <math>1.5 \times \text{ULN} < \text{TBL} \leq 2 \times \text{ULN}</math>
 

LIVER EVENTS	
 
• <math>\text{ALT}</math> or <math>\text{AST} > 5 \times \text{ULN}</math>
 
• <math>\text{ALP} > 2 \times \text{ULN}</math> (in the absence of known bone pathology)
 
• <math>\text{TBL} > 2 \times \text{ULN}</math> (in the absence of known Gilbert syndrome)
 
• <math>\text{ALT}</math> or <math>\text{AST} > 3 \times \text{ULN}</math> and <math>\text{INR} > 1.5</math>
 
• Potential Hy's Law cases (defined as <math>\text{ALT}</math> or <math>\text{AST} > 3 \times \text{ULN}</math> and <math>\text{TBL} > 2 \times \text{ULN}</math> (mainly conjugated fraction) without notable increase in <math>\text{ALP}</math> to <math>> 2 \times \text{ULN}</math>)
 
• Any clinical event of jaundice (or equivalent term)
 
• <math>\text{ALT}</math> or <math>\text{AST} > 3 \times \text{ULN}</math> accompanied by (general) malaise, fatigue, abdominal pain, nausea, or vomiting, or rash with eosinophilia
 
• Any adverse event potentially indicative of a liver toxicity*
 

[figure not shown]
\*These events cover the following: hepatic failure, fibrosis and cirrhosis, and other liver damage-related conditions; the non-infectious hepatitis; the benign, malignant and unspecified liver neoplasms  
TBL: total bilirubin; ULN: upper limit of normal

**Table 14-2 Follow up requirements for liver events and laboratory triggers**

Criteria	Actions required	Follow-up monitoring
Potential Hy's Law case a	
 
• Discontinue the study drug immediately
 
• Repeat LFTs within 24h
 
• Hospitalize, if clinically appropriate
 
• Establish causality
 
• Report to Novartis as an SAE
 
• Complete Liver CRF
 
	ALT, AST, TBL, Alb, PT/INR, ALP and GGT until resolution c (frequency twice a week until resolution, stabilize or return to within baseline values)
ALT or AST > $8 \times \text{ULN}$	
 
• Discontinue the study drug immediately
 
• Repeat LFTs within 24h
 
• Hospitalize if clinically appropriate
 
• Establish causality
 
• Report to Novartis as an SAE
 
• Complete Liver CRF
 
	ALT, AST, TBL, Alb, PT/INR, ALP and GGT until resolution c (frequency twice a week until resolution, stabilize or return to within baseline values)
> $3 \times \text{ULN}$ and $\text{INR} > 1.5$	
 
• Discontinue the study drug immediately
 
	ALT, AST, TBL, Alb, PT/INR, ALP and GGT until resolution c

Criteria	Actions required	Follow-up monitoring
	
 
Repeat LFTs within 24h
 
Hospitalize, if clinically appropriate
 
Establish causality
 
Report to Novartis as an SAE
 
Complete Liver CRF
 
	(frequency twice a week until resolution, stabilize or return to within baseline values)
> 5 to ≤ 8 × ULN	
 
Repeat LFT within 24 hours
 
If elevation persists, continue follow-up monitoring
 
If elevation persists for more than 2 weeks, discontinue the study drug
 
Establish causality
 
Report to Novartis as an SAE
 
Complete Liver CRF
 
	ALT, AST, TBL, Alb, PT/INR, ALP and GGT until resolution c (frequency twice a week until resolution, stabilize or return to within baseline values)
> 3 × ULN accompanied by symptoms b	
 
Discontinue the study drug immediately
 
Repeat LFT within 24 hours
 
Hospitalize if clinically appropriate
 
Establish causality
 
Report to Novartis as an SAE
 
Complete Liver CRF
 
	ALT, AST, TBL, Alb, PT/INR, ALP and GGT until resolution c (frequency twice a week until resolution, stabilize or return to within baseline values)
> 3 to ≤ 5 × ULN (patient is asymptomatic)	
 
Repeat LFT within 24 hours
 
If elevation is confirmed, initiate close observation of the patient
 
	Monitor LFT until resolution c (frequency twice a week until resolution, stabilize or return to within baseline values)
ALP (isolated)		
> 2 × ULN (in the absence of known bone pathology)	
 
Repeat LFT within 24 hours
 
If elevation persists, establish causality
 
Report to Novartis as an SAE
 
Complete Liver CRF
 
	Monitor LFT until resolution c (frequency twice a week until resolution, stabilize or return to within baseline values)
TBL (isolated)		
> 2 × ULN (in the absence of known Gilbert syndrome)	
 
Repeat LFT within 24 hours
 
If elevation persists, discontinue the study drug immediately
 
Hospitalize if clinically appropriate
 
Establish causality
 
Report to Novartis as an SAE
 
Complete Liver CRF
 
	ALT, AST, TBL, Alb, PT/INR, ALP and GGT until resolution c (frequency twice a week until resolution, stabilize or return to within baseline values) Test for hemolysis (e.g., reticulocytes, haptoglobin, unconjugated (indirect) bilirubin)
> 1.5 to ≤ 2 × ULN (patient is asymptomatic)	
 
Repeat LFT within the next week
 
If elevation is confirmed, initiate close observation of the patient
 
	Investigator discretion Monitor LFT within 1 to 4 weeks or at next visit
Jaundice	
 
Discontinue the study drug immediately
 
Hospitalize the patient
 
	ALT, AST, TBL, Alb, PT/INR, ALP and GGT until resolution c (frequency twice a week until

Criteria	Actions required	Follow-up monitoring
	
 
Establish causality
 
Report to Novartis as an SAE
 
Complete Liver CRF
 
	resolution, stabilize or return to within baseline values)
Any AE potentially indicative of a liver toxicity* severe events only SMQ AE	
 
Consider study drug discontinuation
 
Hospitalization if clinically appropriate
 
Establish causality
 
Report to Novartis as an SAE
 
Complete Liver CRF
 
	ALT, AST, TBL, Alb, PT/INR, ALP and GGT until resolution c (frequency twice a week until resolution, stabilize or return to within baseline values

\* These events cover the following: hepatic failure, fibrosis and cirrhosis, and other liver damage-related conditions; the non-infectious hepatitis; the benign, malignant and unspecified liver neoplasms

a Elevated ALT/AST > 3 × ULN and TBL > 2 × ULN but without notable increase in ALP to > 2 × ULN

b (General) malaise, fatigue, abdominal pain, nausea, or vomiting, or rash with eosinophilia

c Resolution is defined as an outcome of one of the following: (1) return to baseline values, (2) stable values at three subsequent monitoring visits at least 2 weeks apart, (3) remain at elevated level after a maximum of 6 months, (4) liver transplantation, and (5) death.

## 15 Appendix 3: Cardiac Alert Threshold Values and Actions

**Table 15-1 Cardiac alert threshold values and actions**

	Values	Actions
QTcF (QTcB for children ≤ 6 years) Cardiac rhythm	QTcB > 500 ms (< 6 years); QTcF > 500 (≥ 6 years). Sustained ventricular tachycardia lasting 30 sec or more, or ventricular fibrillation, or any hemodynamically compromising cardiac arrhythmia	If confirmed by two repeat ECG, check and correct the patient's serum potassium and magnesium immediately. Report as SAE to Sponsor and transmit to eRT immediately for prompt review. Discontinue patient from study therapy. Monitor ECG hourly until at least 2 consecutive hourly ECGs performed are back to baseline
QTcF (QTcB for children ≤ 6 years)  Resting heart rate	Increase from baseline ≥ 60 ms  HR < 50/min with > 25% decrease from pretreatment baseline verified by ECG	If confirmed by two repeat ECG, check and correct the patient's serum potassium and magnesium immediately. Report to Sponsor as AE (unless it meets the SAE criteria as described in Section 7.2.1 ) and transmit to eRT immediately for prompt review.

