**Table 6-2 12-Lead ECG assessments (triplicate) for all patients (PK Run-in Part, Part A and Part B)**

Epoch	Screen		Treatment 														Follow-up						UNS		
	1	99	101						102				199				201	202	203	204	205	299			
Visit Numbers 													EOT Epoch / premature discontinuation									End of Follow up / PSW			
Study Day			1						2				3				4	5	8	15	29	43			
Window			±0 day						±0 day				±0 day				±0 day	+1 day	±1 day	±2 day	±4 days	±4 days			
Time (post-dose) in hours	-24 to <0		0	1	3	6	8	12	18	24	27	30	36	48	51	54	60	68	72	96	168	336	672	1008	
KAF-LUM SDF 1D cohort		x			x	x			x 	x		x 									x			x	
KAF-LUM SDF 2D cohort		x				x 				x	x	x		x							x			x	
KAF-LUM SDF 3D cohort		x				x 				x				x	x	x			x		x			x	
Coartem cohort		x				x 											x				x			x	

**Note: ECG's should be taken in triplicate within 5 minutes after resting for at least 10 minutes in the supine position to ensure a stable heart rate according to the ECG investigator manual. Also, ECG's should be taken before any other procedure taken at the same nominal time point is performed. For Scheduled time ≤ 2 h ± 10 min; 2 to < 24 h ± 30 min; ≥ 24 to 72 h ± 2 h; > 72 h ± 24 h.**

UNS = Unscheduled visit

EOT = End of Treatment

[figure not shown]
PSW = Premature Study Withdrawal

X = assessment to be recorded on clinical data base

 Patients will be admitted to the hospital on Day 1 and will remain in the hospital under close supervision until they are discharged by the investigator or designee on Day 4.

 Visit structure given for internal programming purpose only.

 ECG assessment at this time point to be done for patients in Part A only, ECG assessments will be repeated in case of abnormalities.

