### 6.5.5 Electrocardiogram (ECG)

ECGs should be taken in triplicate within 5 minutes (after 10 minutes rest in the supine position to ensure a stable heart rate according to the ECG investigator manual). The preferred sequence of cardiovascular data collection during study visits is ECG collection first, followed by vital signs, and blood sampling.

The Fridericia QT correction formula (QTcF) should be used for clinical decisions, except for children  $\leq 6$  years, when Bazett formula (QTcB) is recommended.

Triplicate 12 lead ECGs are to be collected with ECG machines supplied by the central laboratory. Initial manual readout will be done locally in order to detect significant safety findings and allow for immediate response if needed. Local readout will be used for inclusion/exclusion purposes as central readout is not available within 24 hours.

In the event that a clinically significant ECG abnormality is identified at the site (e.g., severe arrhythmia, conduction abnormality of QTcF > 500 ms) the SAE must be reported according to the procedure described in [Section 7.2](#). If the patient is hemodynamically compromised, the investigator or a medically qualified person must initiate appropriate safety procedures without delay (for example cardioversion).

If QTcF is > 500 ms or QTcF increases  $\geq 60$  ms from baseline occur at any time, the patient should be assessed at the site and appropriate safety procedures (e.g., electrolyte correction) initiated without delay, if required. In addition two additional ECGs should be collected at 2-min intervals and provided to the central ECG laboratory for confirmation.

Clinically significant abnormalities must be recorded on the relevant section of the medical history/Current medical conditions/AE eCRF page as appropriate.

For 2-3 day regimens, any post-dose average QTc  $\geq 500$  ms will result in patient discontinuation from the treatment if there is a planned subsequent treatment.

Assessments will be done as indicated in the study assessment schedule table. All ECGs will be assessed centrally by an independent and blinded (with age of patient identified) cardiologist.

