#### 7.5 Cardiac Safety Monitoring

To ensure patient safety and fully characterize the cardiovascular safety of the investigational drug, a standardized process for identification, monitoring and evaluation of cardiac events is followed.

The following categories of notable ECG changes will be assessed during the course of the study (irrespective of whether classified/reported as (S)AE):

- QTcF increase from pretreatment baseline  $\geq 60$  ms (QTcB for children  $\leq 6$  years)
- QTcF  $> 500$  ms (QTcB for children  $\leq 6$  years)

Resting heart rate:

- ECG of HR  $< 50$ /min with  $> 25\%$  decrease from pretreatment baseline or
- HR  $< 50$ /min associated with symptoms

Cardiac rhythm:

- Any cardiac arrhythmia associated with hemodynamical compromise
- Sustained ventricular tachycardia  $\geq 30$  sec, or ventricular fibrillation

Every cardiac event as defined in [Table 15-1 in Appendix 3](#) should be appropriately documented in the eCRF (both AE and SAE) and followed up by the investigator or designated personnel at the trial site as summarized in [Appendix 3](#).

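### Protocol Table 15-1 assigns six-year-olds Bazett in the label of the 500 ms alert row but Fridericia in its value cell (minor)

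*Protocol*

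**What the plan says.** Table 15-1 in Protocol Appendix 3 lists cardiac alerts and the action for each. The label of its first row is "QTcF (QTcB for children ≤ 6 years) Cardiac rhythm", and the QTc part of the value cell beside it is "QTcB > 500 ms (< 6 years); QTcF > 500 (≥ 6 years". The action cell opens with "If confirmed by two repeat ECG, check and correct the" and goes on to require electrolyte correction, an SAE report, immediate transmission to the central ECG reader, discontinuation of study therapy, and hourly ECGs until two in a row have returned to baseline.

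The second row has the QTc value "Increase from baseline ≥ 60 ms". Its label also gives QTcB to children of 6 years or less, and its value cell contains no age split. It leads to an AE report (unless SAE criteria are met) and transmission, but not to discontinuation or hourly ECGs.

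Two sections in the body of the protocol set the age rule:

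- Section 6.5.5: "The Fridericia QT correction formula (QTcF) should be used for clinical decisions, except for children" aged 6 or younger, for whom Bazett is recommended.
- Section 7.5: the line beginning "QTcF increase from pretreatment baseline" and the 500 ms line after it both carry a bracket giving QTcB to children of 6 years or less. The section then sends sites to Table 15-1, whose events "should be appropriately documented in the eCRF (both AE and SAE") and followed up as Appendix 3 sets out.

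**The concern.** A site cannot follow both the label and the cell for a child aged 6. The label calls for Bazett and the cell for Fridericia, against the same 500 ms limit. The cell is where the threshold is stated, in the table that Section 7.5 tells sites to act on, so it may well be the text that is used.

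Six-year-olds are eligible. Part B enrols ages 2 to under 12, and its first 4 to 6 children are to be aged 6 to under 12. At heart rates above 60 bpm Bazett gives the larger value, so the cell is the less cautious of the two readings. A confirmed alert could then go without its SAE report, its immediate transmission and its hourly ECGs.

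**Working it through.** **Which wording is the outlier.** The plan gives no figure to reproduce here, so the first step is to set the texts side by side.

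| Place | QTcB applies to | Formula at age 6 |
|---|---|---|
| 6.5.5, general rule | ≤ 6 years | QTcB |
| 7.5, increase of ≥ 60 ms | ≤ 6 years | QTcB |
| 7.5, above 500 ms | ≤ 6 years | QTcB |
| Table 15-1, ≥ 60 ms row label | ≤ 6 years | QTcB |
| Table 15-1, 500 ms row label | ≤ 6 years | QTcB |
| Table 15-1, 500 ms value cell | < 6 years | QTcF |

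Five places agree and one does not. A PDF reading error is unlikely: the two signs in the cell (< and ≥) form a coherent pair, and both would have to be misread, in opposite directions, to have started as ≤ and >.

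**Whether the formula changes the alert.** Using the standard definitions of the two corrections that the protocol names, with RR = 60/HR in seconds:

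- QTcB = QT / RR^(1/2)
- QTcF = QT / RR^(1/3)
- so QTcB / QTcF = RR^(-1/6), which is 1 at 60 bpm and greater than 1 at any faster rate.

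Heart rates are assumed. They are the limits of the two normal ranges in SAP Table 2-3 that meet at age 6 (65 to 110 and 60 to 95 bpm).

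Example: QT 400 ms at 95 bpm. RR = 60/95 = 0.6316.

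- QTcB = 400 / 0.7947 = 503 ms, above 500
- QTcF = 400 / 0.8580 = 466 ms, below 500

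The label gives an alert and the cell gives none. The range of QT over which the two readings disagree is:

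| Heart rate (bpm) | QT at which QTcB = 500 (ms) | QT at which QTcF = 500 (ms) | Width (ms) | QTcF when QTcB = 500 (ms) |
|---|---|---|---|---|
| 60 | 500.0 | 500.0 | 0 | 500.0 |
| 65 | 480.4 | 486.8 | about 6 | 493.4 |
| 95 | 397.4 | 429.0 | about 32 | 463.1 |
| 110 | 369.3 | 408.5 | about 39 | 452.0 |

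**Which actions are recovered elsewhere** for a six-year-old with confirmed QTcB above 500 ms and QTcF at or below 500 ms:

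- *Discontinuation.* Section 6.5.5 has its own rule: in 2- and 3-day regimens an average post-dose QTc of 500 ms or more stops treatment if a dose is still planned. Read with that section's recommendation of Bazett up to age 6, it covers this child.
- *SAE report.* Appendix 1 and the 500 ms examples in 6.5.5 and 5.7.2 name QTcF alone. What remains is the investigator's judgment that an ECG abnormality is clinically significant.
- *Transmission to the central reader.* The ≥ 60 ms row requires it, but only if the rise from baseline is that large.
- *Hourly ECGs.* These are specified only in the 500 ms row.

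**The case against.** The strongest reply is that the documents already settle the point. Everything except one cell says ≤ 6 years, 6.5.5 is the governing rule for clinical decisions, and a careful site would follow it. That stands as to intent, and it is why the point is minor. It does not make the cell correct, and the 500 ms wording in 5.7.2 and Appendix 1 names only QTcF, so it does not bring a site back to Bazett.

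It can also be said that the size is unknowable. That stands too. The protocol does not say how age is counted, gives no age distribution for Part B, and offers nothing from which to estimate how often a confirmed ECG would fall between the two formulas.

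A reader might infer more: that six-year-olds would go on being dosed with QTcB above 500 ms. One might support this by taking the Part B ECG times in Table 6-2 (leaving out those marked "ECG assessment at this time point to be done for patients in Part A only") and counting the ECGs that come before a remaining dose. The documents do not support that inference. The separate 6.5.5 rule applies exactly where a dose remains, so such a count does not measure doses wrongly given. Nor is there good support for a Coartem ECG taken at the last dose, at 60 h: SAP Table 5-6 has an ECG window for 68 h and none for 60 h.

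A reader might also suspect that the QTc results are affected. They are not, because SAP Section 2.8.3.1 tabulates QTcF and QTcB categories for all patients.

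**Conclusion.** The concern holds as a minor error: the value cell of the 500 ms row is wrong as written and contradicts its own label, the ≥ 60 ms row label, and Sections 6.5.5 and 7.5.

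The effect is limited to Part B children aged 6 with a heart rate above 60 bpm, a confirmed QTcB above 500 ms and a QTcF at or below 500 ms. For them the cell can remove an SAE report, immediate ECG transmission and hourly monitoring. Stopping is largely protected by 6.5.5; I say largely because that section recommends Bazett rather than requiring it, and its stopping rule says QTc without naming the formula.

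The conclusion assumes age in completed years. With exact age, the two cut-offs differ only on the sixth birthday. The QT ranges depend on the assumed heart rates; the direction above 60 bpm does not. Endpoints, Part A and the SAP summaries are unaffected.

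**What to change.** Change the QTc part of the Table 15-1 cell to `QTcB > 500 ms (≤ 6 years); QTcF > 500 ms (> 6 years)` and state that age is in completed years. The cost is wording in one table cell, with no change to the ECG schedule, data collection or analysis.

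Optionally, repeat the exception for children of 6 years or less beside the QTcF 500 ms wording in 5.7.2, 6.5.5 and Appendix 1, so that the SAE criterion reads the same everywhere.

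The SAP change history includes an entry after final database lock. If conduct is over, list the six-year-olds with confirmed QTcB above 500 ms and QTcF at or below 500 ms, check them against the SAE reports, and correct the table before it is reused.
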